**Comparison of Electrophysiologic And Ultrasound Guidance For Onabotulinum Toxin A
Injections in Focal Upper Extremity Dystonia And Spasticity**

PI: [name]

NCT02334683

Document Date: 9-2-2014

Protocol

Comparison of Electrophysiologic Guidance and Ultrasound Guidance for Botulinum Toxin Injections

Brief Summary of Research (250-400 words):

This is a study to investigate the use of two targeting techniques for botulinum toxin (BoNT) injection for the treatment of focal hand dystonia and upper limb spasticity: Electrophysiologic guidance, using electrical stimulation, and ultrasound. Subjects will be selected from the clinical programs of both Icahn School of Medicine at Mount Sinai and the National Institutes of Health who are already receiving onabotulinum toxin A injections clinically. The study will consist of four visits. Visit one consists of screening subjects who will then be consented and randomized to one of the two treatment techniques for their onabotulinum toxin A injection: 1) Electrophysiologic guidance using electrical stimulation or 2) ultrasound. Visit 2 will occur at week 4 where the subjects will return for a follow up visit to have blinded evaluator measurements of efficacy and strength and capture safety data. Visit 3 will be at week 12 when subjects will cross over and have the alternate treatment technique during their onabotulinum toxin A injection. Visit 4 will occur at week 16 as the final assessment where subjects will have measurements of efficacy and strength and capture safety data by the blinded evaluator.

1) Objectives:

Research Question:

Hypothesis: Neither Ultrasound or electrical stimulation will not show significant differences in the outcome measures.

1) Improvement in dystonia or spasticity severity on visual analogue scale.

Secondary objectives

1. Duration of the injection procedure
2. Weakness in targeted and adjacent muscles after the procedure
3. Number of needle sticks and needle re-direction within a muscle required for delivery with each technique
4. Side effects with each technique
5. Patient self-reported satisfaction with each procedure
6. Physician global impression of change
7. For dystonia, physician rated "Arm Dystonia Disability Scale"
8. For spasticity, physician rated Modified Ashworth scale
9. Patient discomfort assessed on a visual analog scale.

2) Background

Dystonia is characterized by muscle contractions causing abnormal movements or postures (Albanese, et al., 2013). Focal hand dystonia is a task-specific focal dystonia, occurring with one or several specific actions (Sheehy and Marsden, 1982). Assessment of dystonia depends largely on standardized clinical scales, like the Burke-Fahn-Marsden Dystonia Rating Scale (BFM DRS)(Burke et al., 1985).

Spasticity is an upper motor neuron syndrome associated with lesions of the corticospinal system (Lance, 1981). Causes including traumatic brain injury, spinal cord injury, cerebral palsy, multiple sclerosis or stroke result in an imbalance of excitatory and inhibitory synaptic influences and hyperexcitability of the stretch reflexes. It is typically classified as generalized, regional, multifocal and focal (Ward, 2008). The most widely used assessment method is the Ashworth scale, which quantifies the increased tone across each joint on a scale from 0 (normal) to 4 (fixed position) (Bohannon and Smith, 1987).

Botulinum neurotoxin (BoNT) injection therapy is the most effective established therapy for focal dystonia ([name] et al., 2008). OnabotulinumtoxinA (Botox®, Allergan, Irvine, CA) has been approved by the FDA for treatment of upper extremity spasticity. Numerous controlled trials have shown improvement in muscle tone and functional outcomes using onabotulinumtoxinA in adults with upper extremity spasticity (Teasell et al., 2012).

BoNT injections are ordinarily performed using anatomical landmarks, and additional instrumented localization methods include EMG, electrical stimulation and US guidance. Anatomical localization is insufficient for ideal muscle localization (Schnitzler et al., 2012, Molloy et al., 2002). Studies suggest that electrical stimulation guidance improves muscle localization and targeting (Molloy et al., 2002) and effectiveness of BoNT injection (Ploumis et al., 2013). Ultrasound-guided localization is a more recent development (Alter, 2010), that is gaining wider acceptance. Standardized techniques and additional information sources are now available (Alter et al., 2013).

A limited number of recent studies have attempted a comparison of the currently available injection guidance techniques in spasticity patients (Picelli et al., 2013, Picelli et al., 2012). Within the limits of these studies, it was suggested that ultrasound guidance can improve outcomes of BoNT injections in limb spasticity.

In this study we propose a direct comparison of E-stim-based and US-based injection guidance techniques in patients with focal upper extremity dystonia and spasticity. Both localization techniques are considered standard of care and to date one has not been proved superior to the other. Employing one or the other of the guidance techniques does not, in itself, change the risk/benefit balance of the standard injection treatment, based on currently available data.

3) Setting of the Human Research

This is a study being conducted at two sites: The Icahn School of Medicine at Mount Sinai, New York, NY and the National Institutes of Health, Bethesda, MD. Both sites will recruit from patients who are currently receiving treatments with onabotulinumtoxin A within their clinical practices.

4) Resources Available to Conduct the Human Research

Both sites have many patients that are being treated for focal hand dystonia and upper limb spasticity with onabotulinumtoxin A. Each site will offer the study to their clinical patients by providing a copy of the consent form and answering questions about the study. Each site anticipates randomizing 15 participants for a total of 30 participants for the study. We aim to have an equal number of subjects with upper extremity spasticity and focal dystonia randomized to each sequence of e-stim and US and at each site.

The study teams will have an initial conference call meeting to launch the study once both sites have received IRB approval and all contractual obligations have been fulfilled. Then the sites will have monthly conferences to review the status of enrollment and the study procedures.

Both the Mount Sinai site under [name], and the NIH site under the [name] (NIH/NINDS) have considerable experience with research clinical trials including those with BoNT.

NIH Biosketches will be provided to the IRB and the approved Human Subjects training for the entire study team.

5) Study Design

a) Recruitment Methods

At the Icahn School of Medicine site, patients will be introduced to the research project from the Movement Disorders Program and from Drs. [name]'s [name]'s and [name]'s private practices, and by referral from other health care providers.

At the NIH site, patients will be introduced to the research project from the BoNT clinic, including the neurology and movement disorders practitioners at Suburban Hospital, Holy Cross Hospital, George Washington University Medical Center, Georgetown University Hospital, Johns Hopkins University Medical Center, The Parkinson Disease and Movement Disorders Center of Maryland, University of Maryland and others.

Subjects potentially interested will be provided information about the study, copy of the consent form will be provided which subjects can review and bring home for family or friends to review. They will have the opportunity to contact the investigators at the Icahn School of Medicine or the NIH for questions. We anticipate recruiting a total of 30 subjects with 15 subjects at each site within one year.

b) Inclusion and Exclusion Criteria

Inclusion criteria

- Confirmed diagnosis of focal upper extremity dystonia (FHD) or upper limb spasticity
- Stable onabotulinumtoxinA dose regimen with a stable response as judged by the physician and patient for at least 2 treatment sessions.
- Age 18 and above

Exclusion criteria

- Contraindications to botulinum toxin
- Pregnancy or nursing
- Cognitive impairment that prevents reliable outcome measures of self-report

[figure not shown]
c) Number of Subjects

The study will enroll a total of 30 patients, with 15 patients at each site. Target number of patients to be treated and complete the study will be 18 subjects (to have sufficient statistical power).

d) Study Timelines

This is a randomized cross-over study, with two study sites. 4 outpatient visits of approximately 30-60 minutes each will take place over 16- 24 weeks. All NIH patients will also be enrolled in protocol 85-N-0195, and botulinum injections will be done under that protocol.

An outline of the procedures is depicted in the figure below:

The study anticipates enrollment of the first subject in February 2015. The study team anticipates an enrollment period of approximately 36 months with the last patient to be enrolled Dec. 2020 with the primary analysis completed by June 2021.

Study Endpoints

Outcome measures

Primary outcome measures

Improvement in dystonia or spasticity severity on a physician and patient self-reported visual analog scale.

Secondary outcome measures

- (1) Duration of the injection procedure as follows:
 - (a) E-Stim: time from needle In to needle Out
 - (b) Ultrasound: Time from transducer contact on skin to needleout
 - (c) Number of needle sticks/muscle and needle redirection with muscle for E-stim and US
- (2) Weakness after the procedure in targeted and adjoining muscles
- (3) Side effect incidence with each technique
- (4) Patient self-reported satisfaction with each procedure
- (5) Physician global impression of change
- (6) For dystonia, physician rated “Arm Dystonia Disability Scale”
- (7) For spasticity, physician rated Modified Ashworth Scale in targeted and adjoining muscles
- (8) Patient discomfort assessed on a visual analog scale

e) Procedures Involved in the Human Research

Visit 1 - Screening

At the time of the first visit, the protocol, procedures, and the entire consent document will be discussed with the subjects. If the subjects agree to participate, they will sign the consent form and a copy provided before any screening procedures are initiated. Eligibility will be determined by history and physical examination.

The subjects’ history is reviewed and eligibility established. After signing the consent document, the subjects undergo a standard neurologic evaluation focusing on the dystonia and /or spasticity manifestations. Before each treatment visit, women will be given a urine pregnancy test to confirm they are not pregnant.

Patients are randomized by a computerized system with each site provided the sequence of treatments prior to the patient treatment. Each patient will be scheduled to receive their stable, effective injections based upon prior stable regimen using either: a) Electrophysiologic guidance via electrical stimulation or b) US guidance. The same muscles, dose of onaBoNT-A formulation and dilution used previously during the patient’s clinical session will be employed. This treatment is standard of care, with the purpose of measuring the two different targeting techniques. One injector and one blinded rater will be assigned for all of those taking part in the study. Both having comparable experience with the necessary procedures. Every effort will be made to reduce the patients discomfort during the process of measuring the two different muscle targeting techniques. Each injection site (as previously established) is approached using whichever above technique the patient has been randomized to. The number of attempts (sticks), and needle redirection or repositioning within the muscle to obtain the correct localization for each injection site will be recorded. Once the injector is satisfied with the placement based on the technique used, the injection proceeds as per standard of care. For e-stim technique, the time from initiation of the procedure (“needle in”) to completion (“needle out”) is documented. This will be measured from the time the needle is first inserted, until the time the injection is completed and needle removed. For US technique, the time from application of

the US probe to the skin to needle out is recorded. During this process of completing the injection the subject will be videotaped at visits 1 and 3. . The subjects will be asked to rate their level of discomfort with the procedure, on a visual analog scale, after the injection is complete.

Visit 2:

The subjects return to the clinic one month after injection, at the anticipated peak effect of ona-BoNT-A therapy. They will complete self-rating forms (Patient Global Impression of Change and Visual Analog scale for pain) and be evaluated by a blinded rater, who will not know what injection technique has been used (the patients will be instructed to withhold that information). The evaluation will include: visual analog benefit scale; visual analog weakness scale; review of side-effects; standardized clinical scale assessment (by clinician): Arm Dystonia Disability Scale for limb dystonia; Ashworth scale for spasticity; Global Assessment of Change/Clinical Global Impression of change; weakness assessed on the MRC scale; weakness of targeted and neighboring muscles as assessed with a mechanical force transducer (standard for both sites).

The blinded rater is the non-injecting neurologist who will be one of the co-investigators who did not participate in the subject's study visit and will remain the blinded rater consistently for the subject for the study. The blinded rater will provide an assessment of dystonia or spasticity without know the muscle targeting method used. The visual analog scales will be used by the blinded rater but the patient will complete a satisfaction scale of the procedure on a 10 point scale (see the attached appendix 1)

Visit 3:

An interval history will be obtained, and a targeted examination repeated. If on re-evaluation the patient's dystonia or spasticity has increased and retreatment is deemed to be clinically indicated then the patient will be re-injected. The muscle pattern and dose will remain the same as on visit one. Muscle localization will be with the second technique (crossover). As in Visit 1, the process of completing the injection of the subject will be videotaped. If on clinical evaluation the patient's severity of the patient's dystonia or spasticity does not require treatment re-injection will be deferred. The patient will return when clinically symptomatic (16-24 weeks), re-evaluated and re-injection will occur when clinically appropriate, as described above.

Visit 4:

This will be identical to visit 2, i.e. 4 weeks post re-injection. The study ends after visit 4.

End of Participation

Subjects will be referred back to their clinical care. If any new information pertaining to the patients' care is obtained during the study, it will be shared with the patients and their healthcare providers.

f) Specimen Banking

No samples are being stored. Data collected for research will be coded and stored on MSSM and NIH secured servers. Only the investigators will have access to the data and only the PI will have access to the code key. Any data that is shared between the sites will be done with a process that is encrypted and de-identified.

g) Data Management and Confidentiality

Data Collection

All data will be collected about each enrolled subject, e.g., Demographics, Standard clinical regimen, medical history, medications, randomly selected targeting method (ultrasound or e-stimulation), results of the blinded rater's review of muscle strength and response to post-treatment. A subject's response about discomfort during the study at each visit. The data will be documented on de-identified documents. This de-identified data will be shared by the two sites using an encrypted process with the NIH site inputting the data points into a statistical software for final analysis. The data to be stored indefinitely will be de-identified data. We will only need the link to patient files until the database is locked. We anticipate the link can be destroyed once the database is locked. This would be approximately 1 year after the last patient's last visit.

Analysis of data/ study outcomes

The investigators have scheduled an initial investigator's meeting (August 8, 2014) where training, data collection and verification process will be defined, protection, encryption, physical controls, and separation of identifiers and a system of data sharing). The intent is to de-identify all shared data, during storage, use, and transmission. Transmission would occur using an encrypted system. Quality control measures would be those which are customary by each research site and reviewed by the principal investigator of each site on a quarterly basis for of all collected data. Aggregate data will be reviewed quarterly by the team and discuss any unresolved outstanding issues to be addressed prior to the next quarterly review. Once all data is collected, the study team will review the completed data, address any items that need clarification. Data will be finalized and locked once all information is confirmed by each site and all outstanding queries have been resolved.

Repeated measures ANOVA will be used for the primary outcome. Patients who do not complete all 4 visits will be replaced, and all subjects will be included in the safety analysis. We will use $p < 0.05$ as significance threshold. No interim analysis is planned.

Power analysis

Calculations are based on a α of 5% and a β of 80%, and the published SD for ona-BoNT-A therapy of 20%. There is an expected variation of 15% for the procedure. We hypothesize that US will demonstrate non-inferiority in comparison to E-stim based on previous experience performing the procedures. A total of 18 subjects (9 from each site) are needed to show the desired 15% variation. 15 subjects will be enrolled at each site to allow for screen failures and dropouts.

h) Provisions to Monitor the Data to Ensure the Safety of subjects

Adverse events will be reviewed at every visit. Patients will be asked specifically about pain or weakness. Patients will also have the option to contact the investigators between scheduled visits to report unanticipated events.

The procedures will be stopped if an individual reports any unexpected adverse event NCI grade 3 or higher.

Serious or unexpected adverse events and other unanticipated problems will be reported orally as soon as possible and in writing within 7 days if life-threatening and within 15 days otherwise. Expected or non-serious adverse events will be reported at the time of continuing review. Adverse events will be reviewed at every visit. Patients will be asked specifically about pain or weakness. Patients will also have the option to contact the investigators between scheduled visits to report unanticipated events.

The procedures will be stopped if an individual reports any unexpected adverse event NCI grade 3 or higher.

Serious or unexpected adverse events and other unanticipated problems will be reported orally as soon as possible and in writing within 7 days if life-threatening and within 15 days otherwise. Expected or non-serious adverse events will be reported at the time of continuing review.

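### Injection duration is timed from needle in for E-stim but from transducer contact for ultrasound, and no common start or ultrasound needle-in time is planned, so the two durations are not on one scale

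*Combined protocol and SAP*

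**What the plan says.** Under Study Endpoints in section 5(d), secondary outcome (1) gives each technique its own definition of duration. For E-stim it is "E-Stim: time from needle In to needle Out". For ultrasound it is "Ultrasound: Time from transducer contact on skin to needleout".

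The Visit 1 procedures in section 5(e) repeat both. The E-stim wording begins "For e-stim technique, the time from initiation of the procedure", equates that initiation with needle in, and adds: "This will be measured from the time the needle is first inserted, until the time the injection is completed and needle removed". For ultrasound, the interval that starts with application of "the US probe to the skin to needle out is recorded".

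Three other statements in 5(e) bear on the point:
- Counts are kept of needle sticks and of "needle redirection or repositioning within the muscle to obtain the correct localization for each injection site will be recorded".
- "Each injection site (as previously established) is approached using whichever above technique the patient has been randomized to".
- "During this process of completing the injection the subject will be videotaped at visits 1 and 3".

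Duration is the first of the nine secondary objectives in section 1. Section 5(g) names an analysis method for the primary outcome only. No expected duration, standard deviation or difference in duration is given anywhere.

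**The concern.** The trial compares two ways of finding the muscle, and procedure time is one of the practical outcomes on which they may differ. Ultrasound scanning before the needle goes in is counted. Any palpation or landmarking before the needle goes in for E-stim is not. A reported difference in minutes would combine a difference between techniques with a difference in when the clock was started, and the planned data would not let a reader separate the two.

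Randomization and crossover do not help, because the start rule goes with the technique in every patient and both periods. A larger sample would only estimate the same mixed quantity more precisely.

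The protocol also does not say whether timing is per muscle or per session. That decides whether the difference in start enters once or at every muscle.

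**Working it through.** The plan has no duration figure to reproduce, so the check is algebraic. The clock definitions come from 5(d) and 5(e). The components are those that the definitions imply.

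**Components for one timed interval**
- AE: E-stim work on the limb before needle in (not counted)
- NE: E-stim needle in to needle out (counted)
- AU: ultrasound work on the limb before probe contact (not counted)
- SU: ultrasound scanning from probe contact to needle in (counted)
- NU: ultrasound needle in to needle out (counted)

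**Step 1. Recorded difference, ultrasound minus E-stim**

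R = (SU + NU) − NE

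**Step 2. Against needle in to needle out for both**

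D_needle = NU − NE, so R − D_needle = SU.

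SU cannot be negative if the probe is applied before the needle. The direction is therefore fixed, and the size is not given.

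**Step 3. Against a common localization start to needle out for both**

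D_common = (AU + SU + NU) − (AE + NE), so R − D_common = AE − AU.

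The documents give neither term. The sign is open. Because the injection sites are already established for each patient, both terms may be small.

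**Step 4. Is needle in to needle out a neutral yardstick?**

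D_needle − D_common = (NU − NE) − (AU + SU + NU − AE − NE) = AE − AU − SU.

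If AE = AU, the planned difference R equals D_common exactly, while D_needle is too low by SU. The reason is that E-stim localizes with the needle already in, and the redirections recorded under 5(e) fall inside NE, whereas ultrasound can localize before insertion. Needle in to needle out alone is not neutral, and replacing the planned clocks with it would not solve the problem.

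**Step 5. Per muscle or per session**

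If each muscle is timed separately and the times are summed, AE − AU enters once per muscle. If one clock runs from the first start event to the last needle out, work on the second and later muscles falls inside both clocks, and only the first muscle contributes. The text supports either reading.

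**Step 6. Can the missing times be recovered?**

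Not with assurance. No ultrasound needle-in time and no E-stim localization start are listed for recording. The videos at Visits 1 and 3 might show them, but 5(e) ties filming to completing the injection, with no stated starting point and no timing use. Section 6 makes video subject to a separate agreement. The investigators' meeting in 5(g) is to define data collection, but nothing says that it settles the start event.

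**The case against.** The strongest defence is that the rule is coherent. It is stated the same way in the outcome list and the procedures, so it is neither a slip nor a contradiction. The procedures treat needle in as the start of the E-stim procedure, which suggests that each clock runs from first use of the guidance tool: the stimulating needle or the probe. On that reading scanning is a real time cost of ultrasound and belongs in its total, and E-stim searching is counted too. The documents describe no separate E-stim palpation step, and section 2 presents anatomical landmarks as the ordinary basis of these injections, not as something particular to E-stim. Being listed first is not a stated ranking, and the hypothesis in section 1 leads directly into the visual analog outcome, so tying it to duration is arguable.

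Most of this stands. It rules out two stronger readings that a reader might infer:
- **That the plan is biased against ultrasound.** The one-way offset SU exists only against needle in to needle out, which Step 4 shows is not neutral. Against a common start the sign is unknown.
- **That the start rule is likely to produce a false significant difference.** The documents give no procedure time, no standard deviation for duration and no test for this outcome, so no such probability can be attached to this trial.

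What does not stand is the view that nothing needs changing. The rationale is not written down, any E-stim work before insertion is uncounted, and without an ultrasound needle-in time scanning cannot be separated from needle time.

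**Conclusion.** The point holds as a minor gap in how a secondary outcome is defined. As planned, the recorded difference is not a needle-in-to-needle-out comparison. It matches a common-start comparison only if work before the clock starts is equal under the two techniques, which the plan neither states nor records. The departure is SU against the first yardstick and AE − AU against the second. Neither size is given, and the second may be near zero.

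The algebra assumes only that the probe touches the skin before the needle goes in and that needle out is the same event for both techniques. The different starts may be deliberate, and the documents do not support calling them an error. The primary visual analog outcome, safety and the sample size are unaffected. It is a cheap improvement that makes the duration comparison interpretable.

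**What to change.** In sections 5(d) and 5(e):
1. Keep the two planned clocks. If they are meant to run from first use of each guidance tool, say so.
2. Add a first-needle-in time for ultrasound.
3. Add one common start time for both techniques, with a written definition: first contact with the limb to locate the target muscle.
4. State whether timing is per muscle or per session.
5. Report common start to needle out as the like-for-like comparison, with needle in to needle out and the planned tool-specific interval alongside it.

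The cost is a wording change and one or two extra times per procedure: one for E-stim, and two for ultrasound unless probe contact is itself the first contact. No visit or procedure is added. The drawback is that the common start is a softer, observer-judged event for E-stim than needle in, which is why it needs the written definition and why the planned clocks should be kept beside it.

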- Treatment of BoNT to subjects with breathing or swallowing problems poses substantial risks. Muscles in the neck that help in breathing and swallowing may be over relaxed. Subjects may experience severe breathing problems, and inability to swallow. Food and water may also enter the lungs. This potential risk is limited in this study because the muscles being injected are not in the neck but in the arm and hand.
- Allergic reaction, and/or skin or eye irritation
- Nausea
- Skin inflammation (dermatitis)
- The spread of BoNT may be life-threatening and may even lead to death, but this would be a rare occurrence due to the location of the study drug being injected.
- Bad effects have been seen in pregnant animals who were given Botox. Please tell your study doctors immediately if you get pregnant while on this study. If you become pregnant, you will be removed from the study.
- Risk of being videotaped is loss of confidentiality. To reduce this we will not include any personal information, such as your name, with the recording. We will discuss this with you prior to any recording and we will ask you to sign a separate video agreement for this.

There is no difference in procedures and associated risks due to participation in this protocol then treatment for clinical care.

There is some discomfort and local pain associated with insulated EMG injection needles or wire insertions as well as with the current delivered during electrical stimulation. Some patients have discomfort for 1-3 hours after hooked wire insertion, but most tolerate the procedure well. Patients are free to discontinue diagnostic testing or injection at any time.

There is no medical risk with ultrasound. There may be mild discomfort or skin irritation with the coupling gel used on the transducer.

There is a very small risk that the muscles will not be targeted equally due to using only one of the targeting methods to identify the muscle and subject could possibly not have results of previous clinical treatments.

There is a risk should a subject be pregnant or become pregnant during the study. These risks are unknown and could minor or major (death). Women of childbearing potential will have a pregnancy test prior to treatments and reminded to continue to use two forms of contraception. Men should not father a child while on this research study and will be requested to use condoms while participating in this study.

The patients have a potential risk for loss of privacy

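### The blinded rater also takes the side-effect history at Visits 2 and 4, which may reveal the guidance technique or lead patients to under-report guidance-related symptoms

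*Combined protocol and SAP*

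**What the plan says.** Section 5e (Visit 2) has the patient assessed about one month after injection by a rater kept unaware of the technique. On the content of that assessment it states: "The evaluation will include: visual analog benefit scale; visual analog weakness scale; review of side-effects; standardized clinical scale assessment". The list goes on to the global assessment of change, MRC strength and force-transducer measurements. To keep the rater blind, "the patients will be instructed to withhold that information". The rater is a co-investigator who did not inject and who "will remain the blinded rater consistently for the subject for the study". For Visit 4 the section says: "This will be identical to visit 2, i.e. 4 weeks post re-injection". The Brief Summary agrees, giving the blinded evaluator both the efficacy and strength measurements and the safety data at the final visit.

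Section 5h adds, for adverse-event review at every visit: "Patients will be asked specifically about pain or weakness". Section 6 attributes discomfort and local pain to needle or wire insertion "as well as with the current delivered during electrical stimulation", and says of ultrasound: "There may be mild discomfort or skin irritation with the coupling gel used on the transducer".

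Under Study Endpoints, the primary outcome is a visual analog rating by physician and patient, and secondary outcome (3) is the incidence of side effects by technique.

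**The concern.** The patient knows which technique was used, and the rater must not. A side-effect interview is a conversation in which the patient is invited to describe what the procedure did to them. If the patient mentions a reaction to the current or to the gel, the rater has in effect been told the technique. If the patient takes the instruction to withhold more broadly than intended, the symptom may go unmentioned.

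The first outcome weakens the blind behind the physician's part of the primary outcome, the global impression, the Ashworth or Arm Dystonia rating and the strength ratings. The second leaves gaps in secondary outcome (3), and those gaps would fall on the symptoms most closely tied to the guidance method. The rater's blind does not protect the patient's own ratings in any case, so the physician-rated outcomes are the ones at stake.

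**Working it through.** The plan gives no figure on this point, and the sample size of 18 completers does not enter into it. The check is to set the relevant sections side by side and trace which ratings a disclosure could reach.

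1. **Who takes the history.** Section 5e (Visit 2) puts the side-effect review inside the blinded rater's evaluation, Visit 4 repeats Visit 2, and the Brief Summary assigns safety data to the blinded evaluator. The available text names no one else for this task at these visits.

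2. **What could disclose the technique.** Section 5h requires a direct question about pain or weakness. Section 6 links the stimulation current to one technique and the coupling gel to the other. A bare report of pain or skin irritation does not discriminate, because Section 6 also lists injection pain and skin irritation as general risks. Disclosure needs the patient to describe the cause, such as the current or the gel.

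3. **What safeguards exist.** The instruction to patients is the only one described. The text sets no order of rating, no script for side-effect questions and no check of whether blinding held.

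4. **Which ratings are exposed.** Each patient receives both techniques, one per period, so knowing the first identifies the second. The Visit 2 list prescribes no order. Suppose it is followed as written: the benefit and weakness scales come before the side-effect review, and the clinical scales, global impression and strength measures come after it.

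| Disclosure during the side-effect review at | Order as listed | All ratings signed first | History taken by someone other than the rater |
|---|---|---|---|
| Visit 2 | Visit 2 clinical scales, global impression and strength; all Visit 4 ratings | All Visit 4 ratings | None by this route |
| Visit 4 | Visit 4 clinical scales, global impression and strength | None | None by this route |

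Two things follow. The Visit 2 benefit rating is not exposed if the listed order is kept. Signing ratings first closes the route within each visit, but not the route from Visit 2 to Visit 4. That second route is reduced only by neutral questioning or closed by a different history-taker.

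5. **Direction and size.** The documents give no rate of disclosure and no estimate of how far knowledge of the technique would shift a rating. Direction is also open. The Background cites studies suggesting better outcomes with ultrasound in limb spasticity, the Objectives expect no significant difference, and the power section expects ultrasound to be non-inferior. No numerical bias can be derived from this.

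**The case against.** The strongest reply is that the instruction covers which technique was used and says nothing about symptoms. A patient can obey it and still report pain or a rash, and such a report fits either technique. That stands. A reader might infer that every side-effect answer must either reveal the technique or be suppressed, and the documents do not support this.

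Timing also helps the plan. The symptoms in question are mostly procedural, the one duration given (1–3 hours) is for hooked-wire placement, and the rater sees the patient four weeks later. Discomfort is rated immediately after injection at Visits 1 and 3, an interval history is taken at Visit 3, and patients may contact the investigators between visits. These points reduce the risk without removing it: a discomfort scale is not a side-effect history, contact between visits is optional, and after the second injection Visit 4 is the only scheduled follow-up.

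Blinded collection of side effects is also a defensible choice in itself. Moving the history to the injector, or to anyone else who knows the technique, would protect the efficacy ratings and leave a comparative safety outcome ascertained without blinding. This stands too, and it is why reassignment is offered below only as an option.

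A reader might also try to put a number on the bias. If 10–50% of patients disclosed and each disclosure moved the paired benefit difference by 5–15 points, the mean would shift by 0.10 × 5 = 0.5 to 0.50 × 15 = 7.5 points. Neither input comes from the documents. The upper end combines both extremes and needs every shift to go the same way, so the range should not be set against the 15% variation in the power section.

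**Conclusion.** The point holds as a risk. At Visits 2 and 4 the person whose blind protects the physician-rated outcomes also conducts the interview most likely to break it, and the only safeguard described is the patient's discretion. Disclosure at Visit 2 would carry to every Visit 4 rating, because the rater stays the same and only two techniques are used. Under-reporting of guidance-related symptoms is possible, but nothing in the documents shows that it will happen.

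The size of either effect cannot be estimated from the documents. The conclusion assumes that patients know which technique they received, which the instruction to withhold implies. It also assumes that the opening items of the safety-monitoring list, which are missing from the text available here, do not assign the history to someone else. The case for acting rests on the low cost of the remedy rather than on a demonstrated bias.

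**What to change.** Amend Section 5e (Visit 2), which also governs Visit 4:

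- The rater records and signs all benefit, global, clinical-scale and strength ratings before any side-effect question is asked.
- Side effects are elicited with a short script in technique-neutral wording that does not ask about the stimulator, current, probe or gel.
- Patients are told that the instruction to withhold covers only the name of the technique and that every symptom should be reported.

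This costs a reordered case report form, a script and a sentence of patient instruction, with no new staff, visit or procedure.

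It leaves some exposure from Visit 2 to Visit 4. To limit that, an existing team member other than the rater may take the side-effect history with the same script and keep the answers from the rater. This needs that person for a few minutes at each of the two visits. If that person knows the technique, secondary outcome (3) is no longer ascertained blind, and the protocol should state which arrangement was chosen and why.
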